11.8 Patient Discontinuation and Replacement

Patients are free to terminate their participation (with or without reason) in the study at any time. Likewise, a patient may be terminated from the study by the investigator or the Sponsor, MicroCube, at any time if either investigator or Sponsor determines that it is not in the patient's best interest to continue participation. Enrolled patients that are terminated because of lack of compliance to protocol will not be replaced and will be considered lost to follow-up. If a patient is terminated prior to the 12-month follow up visit, this patient will be considered a treatment failure.

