13.6.2 Contraception

The patient must be on a reliable method of contraception for the duration of the study. Special attention should be paid to medication review of hormonal contraception since the patient must have been on said method for \geq 3 months prior to the onset of the screening menstrual cycle used for PBLAC diary completion and must remain on the same hormonal regimen through the 12-month follow-up visit.

CONFIDENTIAL & PROPRIETARY

Also, a subject may not begin hormonal contraception during the follow-up period if she were not on one at the time of screening.

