13.11.3 Sanitary Products

The Sponsor will provide the sanitary product inventory for study staff to distribute to each patient. Patients are required to exclusively use the sanitary products provided at screening through the 12-month follow-up visit. Every effort should be made to ensure that all patients comply with this requirement.

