17.1.1 Intent-to-Treat (ITT) Cohort

All patients who are enrolled in the study (enrollment defined as patients who met all study eligibility criteria and in whom the procedure is initiated) are included in the Intent-to-Treat (ITT) cohort.

The ITT cohort will be used for the following analyses (as defined in Section 9.1 & 9.2):

- Primary safety and effectiveness analyses at 12-month follow-up visits.
- Safety & effectiveness analyses at 24, and 36-month follow-up visits.

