17.1.2 Per Protocol (PP) Cohort

This cohort consists of all ITT Patients who are considered treatable patients, completed ablation therapy and attended 12-month follow-up visit.

The PP cohort will be used for the following analyses:

- Safety and efficacy outcome measures at 12, 24, and 36-month follow-up visits
- Secondary Analyses to assess amenorrhea rates, improvement of quality of life, evaluate patient and user (investigator) satisfaction.
- Subgroup Analyses
- Exploratory Analyses

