17.2 Analysis of Primary Efficacy Endpoint at 12-month

The primary efficacy endpoint is binary (success/failure). Success is defined as PBLAC score of \leq 75 at the 12-month follow-up assessment without incidence of additional interventions or treatments for bleeding prior to the 12-month follow-up visit. The proposed study's primary hypothesis is:

Null Hypothesis (H₀) = $p_{minitouch} \le OPC$

Alternate Hypothesis (H₁) = p_{minitouch} > OPC

where p_{minitouch} is the Minitouch Endometrial Ablation System success rate and OPC is 66% which is the FDA identified objective performance criterion (OPC) for global endometrial ablation (GEA) devices.

The exact binomial test will be conducted to compare the investigational device success rate to OPC minimum success rate for effectiveness. To achieve study success the measured success rate should exceed the 66% OPC.

ITT with imputation will be utilized to test the primary hypothesis, such that all missing data are failures for the primary endpoint. The following imputation techniques will be conducted for sensitivity analysis:

- Multiple Imputation (MI) using fully conditional specification (FCS) method, in which logistic regression is used to predict whether the missing value is likely to be a success or failure. The number of imputations will depend on the fraction of missing information.
- Tipping point, in which the numbers of successes or failures amongst missing data necessary to meet the primary endpoint hypothesis are determined.

Fisher-Freeman-Halton test will be conducted to compare the success rates between investigational sites. Results will also be stratified and compared across relevant baseline characteristics including demographics.

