20.2.2 Protocol Deviations

All protocol deviations will be classified as major or minor and documented and discussed in the Clinical Study Report.

A deviation is defined as any departure from clinical study requirements, including those cited within Good Clinical Practice (GCP) guidelines. Protocol deviations that affect the rights, safety, or welfare of human Patients must be reported to the study Sponsor as soon as possible from the occurrence of the deviation.

Major protocol deviations are defined as any protocol deviation that affects the soundness of the data or a Patient's rights. A major protocol deviation is non-compliance with the approved protocol and trial requirements that may impact patient safety, affect the integrity of the data and/or affect the patient's willingness to participate in the study.

Examples may include:

- Failure to meet all entry criteria;
- Non-compliant with device treatment regimen

A **minor** protocol deviation is non-compliance with the approved protocol and a trial requirement that does not impact Patient safety, compromise the integrity of the data and/or affect the Patient's willingness to participate in the study.

Protocol deviations must be reported to the IRB per the Institutional Review Board's reporting requirements. The occurrence of protocol deviations will be monitored by the study Sponsor and

Page 53 of 65

CONFIDENTIAL & PROPRIETARY

designee for evaluation of Investigator compliance to the study protocol, GCP guidelines, and regulatory requirements. Protocol deviations will be reviewed and evaluated by the study Sponsor or designee on an ongoing basis in accordance with the Protocol Deviation Management Plan, as applicable.

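### The Per Protocol cohort is in effect a completers set: it requires month-12 attendance but ignores post-treatment deviations that make the month-12 PBLAC unsound

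*Combined protocol and SAP*

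**What the plan says.** Section 17.1.2 defines PP in one sentence: "This cohort consists of all ITT Patients who are considered treatable patients, completed ablation therapy and attended 12-month follow-up visit". It assigns to PP the safety and efficacy outcomes at 12, 24 and 36 months and the secondary, subgroup and exploratory analyses. Section 17.7 confirms that subgroup results, at all three time points, use PP only.

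PP is a subset of ITT, which section 17.1.1 builds on "enrollment defined as patients who met all study eligibility criteria and in whom the procedure is initiated". For the primary test, section 17.2 says "ITT with imputation will be utilized to test the primary hypothesis, such that all missing data are failures for the primary endpoint". Section 11.8 adds: "If a patient is terminated prior to the 12-month follow up visit, this patient will be considered a treatment failure". Sections 9.1 and 17.2 also count as a failure any woman who had a further intervention or treatment for bleeding before month 12.

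Two post-treatment rules protect the PBLAC as a measurement. Section 13.11.3: "Patients are required to exclusively use the sanitary products provided at screening through the 12-month follow-up visit". Section 13.6.2, on women using hormonal contraception: "must remain on the same hormonal regimen through the 12-month follow-up visit"; women not using it at screening may not start it during follow-up. Section 12.8 gives the month-12 visit a window of 4 weeks either side and asks for the diary within it.

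Section 20.2.2 grades every deviation as major or minor, and major includes "any protocol deviation that affects the soundness of the data". Section 17 does not refer to that grading.

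**The concern.** A per-protocol analysis is normally read as the result among women who were treated and measured as the protocol requires. This set selects mainly on something else, namely whether the woman came back at month 12. Women who did not come back are nearly all failures in ITT, so removing them mostly raises the success rate. Women who came back with a PBLAC made unreliable by other sanitary products or a change in hormones are kept, and their score is taken at face value.

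At stake are the supportive 12-month result, the PP results at 24 and 36 months, the secondary and exploratory summaries, and every subgroup table. All would carry a label that the definition does not earn. None could show whether the result holds among women whose outcome was validly measured.

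**Working it through.** **1. Which breaches the definition catches**

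| Situation | Treatment in PP as written |
|---|---|
| Entry criterion not met | Largely removed, because ITT requires eligibility. Some doubt remains: section 11.8.1 treats a late-found exclusion as a deviation, not a termination, and 'treatable' is undefined |
| Ablation not completed | Removed |
| Treated for bleeding before month 12, attended | Kept, counted as failure (9.1, 17.2) |
| Treated for bleeding before month 12, then left | Removed, although a failure in ITT |
| Hormonal contraception started or changed for reasons other than bleeding, attended | Kept, scored on PBLAC |
| Non-study sanitary products, attended | Kept, scored on PBLAC |
| Month-12 diary outside the window, attended | Kept; no window condition |

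The gap therefore lies in the last three rows (deviators kept) and in the fourth (true failures dropped).

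**2. The plan's own sample size**

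Inputs from section 17.2.1: null rate 0.66, expected rate 0.78, one-sided alpha 0.025, power 80%, normal approximation with null variance.

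n = [(1.960 × √(0.66 × 0.34) + 0.842 × √(0.78 × 0.22)) / (0.78 − 0.66)]² = 113.26, so 114. This reproduces the stated figure.

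Allowing 10% dropout, 114/0.9 = 126.67, against 126 stated. I use the plan's figures: 126 treated, 126 − 114 = 12 lost, and 0.78 × 114 = 88.9, so 89 successes. I assume that the 12 lost have no usable PBLAC and that all 114 attenders have one.

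**3. Effect of the attendance condition alone**

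- ITT, missing as failure: 89/126 = 70.6% (exact one-sided p against 66% = 0.158).
- PP as written: 89/114 = 78.1% (p = 0.0034).
- Difference: 7.4 points before rounding.

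The gap depends on the loss, holding success among completers at about 78%:

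| Lost | ITT | PP | Gap (points) |
|---|---|---|---|
| 6 | 94/126 = 74.6% | 94/120 = 78.3% | 3.7 |
| 12 | 89/126 = 70.6% | 89/114 = 78.1% | 7.4 |
| 20 | 83/126 = 65.9% | 83/106 = 78.3% | 12.4 |

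At n = 126 the exact test needs 94 successes (actual alpha 0.0239). A trial that just misses on ITT, at 93/126 = 73.8%, would show 93/114 = 81.6% in PP if 12 were lost.

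**4. Effect of also excluding deviators**

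The documents give no expected number of deviators, so k is assumed. The bounds are (89 − k)/(114 − k) if all were successes and 89/(114 − k) if none were.

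| k | All successes | None successes |
|---|---|---|
| 5 | 84/109 = 77.1% | 89/109 = 81.7% |
| 10 | 79/104 = 76.0% | 89/104 = 85.6% |
| 15 | 74/99 = 74.7% | 89/99 = 89.9% |

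If deviators succeed at the same rate as the others, PP stays at about 78.1%.

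**5. Effect of keeping treated-then-left women as failures**

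If m of the 12 lost had been treated for bleeding before leaving, the rate is 89/(114 + m). For an assumed m = 4 this is 89/118 = 75.4%.

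**The case against.** The strongest reply is that no decision rests on PP. The primary hypothesis is tested on ITT with missing data as failures. Section 17.1.1 also assigns 24- and 36-month safety and effectiveness to ITT, and sections 17.6 and 17.7 test no hypotheses for secondary endpoints or subgroups. This stands, and it limits the point to supportive and descriptive results.

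Four stronger readings are tempting, and the documents do not support them.

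- A reader might infer that PP is the only second look at 12-month efficacy. Section 17.2 also plans multiple imputation and a tipping-point analysis. Those address missing scores, though, not scores that are present but unsound.
- A reader might infer that PP has no adherence condition at all. The eligibility requirement in ITT and the completed-ablation requirement address both examples of a major deviation in section 20.2.2, at least in part.
- A reader might infer that the set is tilted toward success from both sides. Only the attendance side has a predictable direction. Nothing in the documents says that deviations lower the PBLAC, and the bounds in the working run both ways.
- A reader might infer that any woman with a hormonal change should be excluded. If the change was treatment for bleeding she is already a failure, and excluding her would raise the rate.

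Two further limits stand. Section 17 opens by leaving the full description of data sets to the SAP, so the deviation grading might be used in text not shown here. And the attendance condition, which produces the gap between ITT and PP, stays under the proposed wording except for women treated for bleeding who then left. That is why the label matters as well as the added condition.

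**Conclusion.** The point holds for supportive results. PP as written conditions on month-12 attendance and not on valid measurement of the month-12 PBLAC, so it is a completers set under another name. With 126 treated, 12 lost and 78% success among completers, attendance alone adds 7.4 points; with 6 or 20 lost it adds 3.7 or 12.4. 'Mostly raises' is as far as this can be put: a woman who missed the visit but sent in her diary could be a success and still be dropped. The number of deviators is unknown, and so is the direction in which excluding them would move the rate. The change is worth making because it is specific and inexpensive, and because the subgroup results have no ITT counterpart in the plan. It does not touch the trial's primary conclusion.

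**What to change.** In section 17.1.2:

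1. Add to the definition: *and had no major protocol deviation (20.2.2) that could affect the 12-month PBLAC, classified before database lock without knowledge of the PBLAC result*.
2. Name at least these: use of non-study sanitary products; hormonal contraception started or changed before month 12 for reasons other than bleeding; a month-12 diary outside the window.
3. State that women who received any intervention or treatment for bleeding before month 12 stay in PP as failures, including those who then left the study. Without this sentence the new exclusion could itself remove failures.
4. If the present definition is kept for any table, label it 'completers'.

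The cost is wording only, since deviations are already recorded and graded. PP becomes slightly smaller, and its rate may move in either direction.

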17.2 Analysis of Primary Efficacy Endpoint at 12-month

The primary efficacy endpoint is binary (success/failure). Success is defined as PBLAC score of \leq 75 at the 12-month follow-up assessment without incidence of additional interventions or treatments for bleeding prior to the 12-month follow-up visit. The proposed study's primary hypothesis is:

Null Hypothesis (H₀) = $p_{minitouch} \le OPC$

Alternate Hypothesis (H₁) = p_{minitouch} > OPC

where p_{minitouch} is the Minitouch Endometrial Ablation System success rate and OPC is 66% which is the FDA identified objective performance criterion (OPC) for global endometrial ablation (GEA) devices.

The exact binomial test will be conducted to compare the investigational device success rate to OPC minimum success rate for effectiveness. To achieve study success the measured success rate should exceed the 66% OPC.

ITT with imputation will be utilized to test the primary hypothesis, such that all missing data are failures for the primary endpoint. The following imputation techniques will be conducted for sensitivity analysis:

- Multiple Imputation (MI) using fully conditional specification (FCS) method, in which logistic regression is used to predict whether the missing value is likely to be a success or failure. The number of imputations will depend on the fraction of missing information.
- Tipping point, in which the numbers of successes or failures amongst missing data necessary to meet the primary endpoint hypothesis are determined.

Fisher-Freeman-Halton test will be conducted to compare the success rates between investigational sites. Results will also be stratified and compared across relevant baseline characteristics including demographics.

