5 PROTOCOL SYNOPSIS

| Title | Minitouch Endometrial Ablation System Treatment for Menorrhagia: An Evaluation of Safety & Effectiveness | | |
|---|---|--|--|
| Short Title | EASE Clinical Trial | | |
| IDE No. | G180282 | | |
| ClinicalTrials.gov Identifier | NCT04267562 | | |
| Protocol No. & Revision | TD18036 v5.0 | | |
| Version Date | 14Dec2021 | | |
| Study Device | Minitouch Endometrial Ablation System ("Minitouch System") | | |
| Proposed Indications for Use | The Minitouch Endometrial Ablation System is intended for ablation of the endometrial lining of the uterus for the treatment of menorrhagia (heavy menstrual bleeding) due to benign causes in premenopausal women for whom childbearing is complete | | |
| Study Design This is a prospective, multi-center, open-label, single-arm, clinical investigation study Design evaluate the Minitouch Endometrial Ablation System in premenopausal women menorrhagia menorrhagia | | | |
| Study Objective | To evaluate the safety and effectiveness of the Minitouch System | | |
| Study Duration | At least 37 months, including an estimated one month of pre-enrollment assessment and 36 months post-treatment follow up | | |
| Planned Number of Sites | Approximately 10 sites from the United States only | | |
| Planned Enrollment | Up to 126 premenopausal women with menorrhagia | | |
| Primary Effectiveness Endpoint | Percent of patients demonstrating reduction of menstrual flow as evidenced by a Pictorial Blood Loss Assessment Chart (PBLAC) score of \leq 75 at the 12-month post procedure time point | | |
| Study Success | To achieve study success, 12-month success rate should exceed the 66% Objective Performance Criterion (OPC) developed by the FDA, outlined in correspondence of Oct 29, 2015 ⁽¹⁾ | | |
| Primary Safety Measure | Reported rate of device and procedure-related serious adverse events at 12-months post-procedure as adjudicated by the CEC | | |

CONFIDENTIAL & PROPRIETARY

Page 14 of 65

Page 15 of 65

| Secondary effectiveness outcome measures include the following: | | | | |
|---|--|--|--|--|
| | DRIAC: at 6 and 12 months | | | |
| | Monstrual Status at 6 and 12 months categorized by: | | | |
| | Interstrual Status at 6 and 12 months categorized by: | | | |
| | • Amenorrhea: PBLAC score U | | | |
| | ○ Light Bleeding: PBLAC score 0 ≤ 35.0 | | | |
| | • Normal Bleeding: PBLAC score 35.1 to 75.0 | | | |
| | • Eumenorrhea: PBLAC score 75.1 to 99.9 | | | |
| | Menorrhagia: PBLAC score >100 | | | |

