9 STUDY ENDPOINTS

9.1 Primary Effectiveness Endpoint

The primary effectiveness endpoint is a reduction in menstrual blood loss as assessed by the Pictorial Blood Loss Assessment Chart (PBLAC) data, a validated, patient self-reported menstrual diary scoring system. All patients must have a baseline PBLAC score of \geq 150 with a documented history of excessive menstrual bleeding to document a clinical diagnosis of menorrhagia.

An individual patient will be considered a success if the PBLAC score is \leq 75 at 12 months post-procedure without incidence of additional interventions or treatments for bleeding prior to the 12-month follow-up

Page 23 of 65

CONFIDENTIAL & PROPRIETARY

visit. To achieve study success, the lower bound of the 95% CI of 12-month success rate should exceed the 66% Objective Performance Criterion (OPC) developed by the FDA.⁽¹⁾

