17.2.1 Study Power

Utilizing a minimum effectiveness rate of 66% (OPC), an expected success rate of approximately 78% for Minitouch, and a one-sided alpha of 0.025, the study sample size required to obtain at least 80% power is 114 Patients. Assuming a dropout rate of approximately 10% at 12 months, the required enrolled sample size is determined to be 126 Patients.

The 78% investigational device success rate is derived from other GEA studies recently conducted and published. For sample size calculation, Minerva utilized an expected success rate of 78% (Laberge et al. J Minim Invasive Gynecol 2015;7:1169-77) and Aegea utilized an expected success rate of 76% (Levie MD, Chudnoff SG. J Minim Invasive Gynecol 2018; S1553-4650).

Multiple scenarios were used to calculate the sample size. Statistical Analysis Software (SAS) POWER procedure Z test for binomial proportion was utilized with the following fixed scenario elements: normal approximation method, 66% null proportion, 0.025 one-sided alpha, 80% nominal power, and null variance estimate.

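### Section 17.2 and the synopsis set study success at a rate above 66%, while Section 9.1 requires the lower 95% confidence limit to exceed 66%; taken literally, the first rule has a type I error of about 48%

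*Combined protocol and SAP*

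**What the plan says.** The rule for study success appears in three places.

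- Section 9.1 (Primary Effectiveness Endpoint): "the lower bound of the 95% CI of 12-month success rate should exceed the 66% Objective Performance Criterion (OPC) developed by the FDA". The interval method is not named, and the section does not say whether the interval is two-sided.
- Section 17.2 (Analysis of Primary Efficacy Endpoint) sets H0: p ≤ 66% against H1: p > 66% and then says: "The exact binomial test will be conducted to compare the investigational device success rate to OPC minimum success rate for effectiveness". The next sentence is the success criterion: "To achieve study success the measured success rate should exceed the 66% OPC". No alpha is given in that text.
- Section 5 (Protocol Synopsis, Study Success row): "To achieve study success, 12-month success rate should exceed the 66% Objective Performance Criterion (OPC) developed by the FDA". There is no confidence bound here, nor a word such as measured or observed.

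Section 17.2.1 gives the only alpha, in the sample-size text: "a one-sided alpha of 0.025, the study sample size required to obtain at least 80% power is 114 Patients". Section 17.2 also counts all missing 12-month data as failures in the ITT analysis, so the denominator is every enrolled patient, planned at 126.

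**The concern.** A point estimate above 66% does not reject H0: p ≤ 66%. When the true rate equals the OPC, the observed proportion falls above it about half the time. Section 17.2, read as written, would therefore accept a device performing exactly at the unacceptable rate on roughly a coin toss. Section 9.1 holds that risk at about 2.5%.

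The trial is open-label and single-arm, so this one threshold decides the effectiveness conclusion. If the result falls between the two cut-offs, someone has to choose which section governs after the data are known. Pre-specification is meant to prevent exactly that.

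**Working it through.** **Inputs.** p0 = 0.66, p1 = 0.78, one-sided alpha 0.025, power at least 80%, 114 evaluable and 126 enrolled after about 10% dropout, normal-approximation Z test with null variance (all Section 17.2.1); missing = failure and exact binomial test (Section 17.2); lower 95% limit above 66% (Section 9.1).

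**1. The plan's own sample size.**

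n = [(z0.975·√(p0(1−p0)) + z0.80·√(p1(1−p1))) / (p1−p0)]²

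= [(1.960 × 0.4737 + 0.8416 × 0.4142) / 0.12]² = 113.26, rounded up to 114 (power 80.3%). The stated figure reproduces. For dropout, 113.26/0.9 = 125.8 and 114/0.9 = 126.7, so 126 is consistent to within rounding. The sizing assumes a test at one-sided 0.025.

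**2. Cut-offs at N = 126.**

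- Measured rate above 66%: 83/126 = 65.9% fails and 84/126 = 66.7% passes, so 84 successes are needed.
- Exact test at one-sided 0.025: the smallest k with P(X ≥ k | p = 0.66) ≤ 0.025 is 94, since P(X ≥ 93) = 0.0374 and P(X ≥ 94) = 0.0239.
- Two-sided 95% Clopper-Pearson lower limit: 65.23% at 93/126 and 66.08% at 94/126, so again 94. This limit and the exact one-sided 0.025 test are the same rule.

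**3. Operating characteristics (exact binomial, N = 126).**

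| True rate | P(pass), measured rate > 66% (≥ 84) | P(pass), exact test or Clopper-Pearson limit (≥ 94) |
|---|---|---|
| 62% | 16.2% | 0.2% |
| 66% (type I error) | 47.9% | 2.4% |
| 78% (power) | 99.9% | 84.8% |

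At the smallest passing result under the measured-rate rule, 84/126, the Clopper-Pearson lower limit is 57.7%.

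**4. Dependence on N.** At N = 114 the measured-rate rule needs 76 successes and has type I error 48.4%; the exact rule needs 86, with 1.9%. Because counts are discrete, the first figure moves with N (48.1% at 120, 53.0% at 124, 50.4% at 125) but stays near one half.

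**5. Dependence on the interval.** Section 9.1 names no method. At N = 126, Clopper-Pearson and Wilson intervals need 94 successes. Wald needs 93 (its lower limit at 93/126 is 66.1%), with type I error 3.7%. A one-sided 95% Clopper-Pearson limit would also pass 93 (66.6%). The conflict zone is therefore 84 to 93 successes (66.7% to 73.8%), or 84 to 92 under the looser readings.

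**6. Chance of landing in the zone.** If the true ITT rate is 78%, P(84 ≤ X ≤ 93) = 15%. If instead 78% applies only to patients with data, and 10% are missing and counted as failures (an assumption; the plan does not say which rate the 78% is), the ITT rate is 0.78 × 0.90 = 70.2% and the probability is 67%.

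**The case against.** The strongest reply is that the intent is clear. The disputed sentence in Section 17.2 follows formal hypotheses and an exact binomial test, and its own subsection sizes the trial at one-sided 0.025. That test at that alpha gives 94/126, the same cut-off as Section 9.1 with an exact interval. Section 17.1.1 refers back to Sections 9.1 and 9.2 for the primary analyses. A measured-rate rule would have 99.9% power at 78%, so nobody sizing for 80% had it in mind. The sentence can also be read as a necessary condition alongside the test, and the synopsis as a loose summary of H1.

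Much of this stands. Section 9.1 is probably the intended rule, and 48% is the error of the success sentence taken literally, not of the plan taken as a whole. The synopsis is less explicit than Section 17.2, although a success criterion placed on a 12-month success rate most naturally means the observed rate. The upper end of the conflict zone does depend on an unstated interval method.

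None of it removes the conflict. Section 17.2 names a test but gives no alpha beside it and does not tie success to rejecting H0; the only success criterion it states is the measured rate. The reference in Section 17.1.1 concerns which cohort is used and does not override that sentence. The interval method moves the edge of the zone by one patient.

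**Conclusion.** The concern holds. The current text contains two incompatible success rules for the primary endpoint. At N = 126 with missing data as failures, they differ by ten patients (84 against 94 successes) and, at a true rate of 66%, by 47.9% against 2.4% in type I error. The 94 assumes a two-sided 95% Clopper-Pearson interval, or equivalently the exact test at one-sided 0.025; a Wald interval would give 93. Because this is the threshold on which the effectiveness claim rests, it should be settled before the 12-month data are analysed. The hypotheses, the named test, the sample-size alpha and Section 9.1 all point the same way, so the correction brings the success sentence into line with the rest of the design.

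**What to change.** Replace the success sentence in Section 17.2 and in the synopsis with one rule, for example: study success is declared if, in the ITT cohort with missing 12-month outcomes counted as failures, the exact binomial test rejects H0: p ≤ 66% at one-sided 0.025; equivalently, if the lower limit of the two-sided 95% Clopper-Pearson interval exceeds 66% (94 or more successes if N = 126).

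Keep the rule in Section 9.1, but name the same two-sided Clopper-Pearson interval there, so that the test and the interval cannot disagree at the margin. Carry the same sentence into any stand-alone SAP.

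The cost is wording only. Data collection and sample size are unchanged; at a true ITT rate of 78%, 126 patients give 84.8% power under this rule.
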